Utilization outcomes evaluated during the year follow-up are: 1) advanced imaging (MRI or CT), 2) lumbar epidural injection, 3) emergency department visit, and 4) surgery (discectomy, decompression, laminectomy, nerve ablation, fusion). Utilization rates will be summarized on a patient basis (proportions of patients) and as rates over time (total utilization including multiple events per patient), and compared between groups with logistic regression and survival analysis methods for repeated events respectively.¹²⁷ We will compare numbers of patients missing work due to LBP between groups with similar procedures. [*We will examine costs from a societal perspective, collecting both direct and indirect costs using cost diaries. As recommended, we will value cost data with standard unit prices¹³² based on University of Utah clinical research billing rates. Lost work productivity will be costed using methods described by Stewart.^{28,133} Cost diaries document work absence or reduced performance (as a percentage of normal) due to losing concentration, repeating tasks, fatigue, etc, at work due to LBP. Lost productive time will be calculated as the number of days of work absence ("absenteeism") and the number of hours of reduced productivity ("presenteeism") multiplied by the patient's self-reported salary.²⁸ Patients not employed outside the home (homemakers, students) will report absenteeism and presenteeism. Lost productive time will be based on average salary for age- and sex-matched individuals according to the Bureau of Labor Statistics. Sensitivity analyses will be used to examine the impact of differing methods of valuing direct and indirect costs.]*

[We will use parametric and non-parametric methods to compare costs between treatments. As the mean is the most useful statistic to evaluate costs related to treatment implementation,¹³⁴ we will calculate means and standard deviations for direct, indirect and total cost by group. We will explore cost data distributions graphically and statistically. With univariate and multivariate techniques we will examine the relationship between treatment and total cost. As cost data are typically skewed we will use nonparametric bootstrapping methods with 2000 pair-wise replications to compare mean costs and avoid distributional assumptions.¹³⁵ Confidence intervals around the mean cost difference will be calculated with bias corrected and accelerated methods.¹³⁶ Regression analyses will also be used to allow costs to be adjusted for patient factors such as socioeconomic status or co-morbidities. We will perform separate analyses for patients with complete cost data and those with imputed costs. Missing cost data will be handled using MI as described.¹³⁷ MI is preferred for missing cost data over alternatives such as last score forward or mean imputation.¹³⁹ Shortand long-term cost-effectiveness (CE) analyses will be conducted. The short-term analysis will use direct and indirect costs over the first 4 weeks. The effectiveness of these costs will be based on OSW and EQ-5D scores at 4 weeks. Long-term CE analysis will use cost and effect data measured at 1-year. Costs and effects will be measured in the same year; eliminating the need for inflation adjustment or discounts. Once 3 parameters are computed: 1) mean differences in cost and effect between treatments, 2) variances for differences in costs and effects, and 3) covariance between effectiveness and cost difference, the incremental cost-effectiveness ratio or incremental net benefits summarizing the monetary value of the intervention will be calculated.¹⁴⁰ A CE acceptability curve will be used to quantify and graphically depict uncertainty in the analysis.¹⁴² To consider uncertainty in parameters, probabilistic sensitivity analysis will be conducted. To reflect the uncertainties in costs and in effects, a gamma distribution will be adopted.]

Specific Aim #3: "Evaluate moderators of improvement with early physical therapy."

Moderators are baseline variables that interacts with the type treatment to predict outcomes.¹²⁶ We will prespecify potential moderators of improvement with early physical therapy based on theory or preliminary findings suggesting a moderating effect including; 1) symptom centralization at baseline (yes/no), 2) severe baseline disability (baseline OSW <40 or \geq 40), 3) leg pain rated higher than LBP at baseline (leg NPRS > LBP NPRS or leg NPRS \leq LBP NPRS). Mixed effects models described above will be extended by adding interaction terms for moderating variables using separate models for each outcome and each variable. The extended models will be used to provide separate estimates of treatment effects within each level of the moderator and to provide statistical tests of the dependence of treatment effects on the moderator. To mitigate risk of low power in subgroup analyses, the NPRS, for which the study has high power to detect important differences, will serve as the primary outcome for evaluating moderators. We may explore different follow-up points or dependent variables, and may consider additional putative moderators if evidence emerges suggesting a potentially important variable that may provide information to patients and providers about types of patients for whom early physical therapy may be particularly beneficial (or unhelpful).

C.10 Proposed Time Line

The timeline is based on our preliminary estimate of recruiting 8 patients per month. At this rate we need 28 months to recruit 220 patients. We allow 3 months at the beginning of the study to establish procedures and 4 months at the end to complete data analysis, manuscript preparation, etc.

	Month 1 Month 2 Month 3	Month 4 Month 5 Month 6 Month 7 Month 8	Month 9 Month 10 Month 11 Month 12
Year 1	Establish study procedures	Recruit approximately 8 patients per month	
Year 2	Recruit 8 patients per month		
Year 3	Recruit 8 patients per month		Complete follow-up evaluations
Year 4	Complete follow-up evaluations		Data analysis, report writing, etc.

C.11 Sample Size Justification

Assuming at least 90% of patients complete the OSW at 6 months, 110 subjects per group (total = 220) provides at least 86% power to detect a difference of 7 points on the OSW to 6 months, assuming a standard deviation of 16 points (treatment effect = 43.8% of 1 standard deviation). MCID for the OSW has been estimated at 6-8 points.^{83,86} This sample size also provides at least 82% power to detect a treatment effect on the 1-year OSW change assuming the same standard deviation and 80% follow-up. In addition, this sample size provides > 99% power to detect a clinically important difference of 2.0 on the NPRS assuming a standard deviation of 2.4 and at least 80% follow-up. Our prior work with patients with LBP and sciatica indicate these estimates of effect are realistic.^{52,72} Our power calculations are slightly conservative as they assume no information will be obtained from patients with missing outcomes; we can expect slightly smaller minimum detectable effects (i.e. greater power) with MI.

C.12 AHRQ Priority Populations

This project will include subjects from AHRQ Priority Populations including women, children (age 18-21), and minority groups as they are represented in the population from which study subjects will be recruited. Because this project is the first to examine the effectiveness and subsequent healthcare utilization resulting from the management strategies described in this proposal, we are taking a pragmatic approach to recruitment instead of targeting the recruitment specifically towards priority populations. Once more information is known about the effectiveness of these strategies, studies specifically examining translation into priority populations such as individuals in rural regions, low income or minority groups will be possible.

C.13 Limitations and Contingencies

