Healthcare Utilization and Direct and Indirect Costs: [*We will collect both direct and indirect costs due to lost work productivity related to LBP over the 1-year follow-up.*] We will use a cost diary method integrated into the web-based data collection system to collect utilization and cost data. Cost diaries offer advantages in terms of feasibility and validity as compared with patient-reported questionnaires for collecting cost data and provide information at regular intervals instead of relying on patient recall over a long time period, minimizing recall error.¹⁰⁹ [*We will collect cost and utilization data monthly via REDCap using the input options outlined below.*] The cost diary will be modeled on paper-based methods with high compliance (85%) for economic analysis in studies of patients with LBP.^{108,131} This compliance rate is consistent with our experience using this method in our ongoing study. Prior research reports no differences between cost

diaries completed for an entire year and extrapolation of data for limited time periods, indicating a robustness to impute scores for random missing data. Patient-reported cost diary data has been found to generally agree with insurance claims, supporting the validity of the self-report cost and utilization data.¹⁰⁸ [*Each monthly cost diary will ask patients if they have utilized healthcare resources in the past month specifically for LBP in 4 categories: 1) provider visits (traditional or complementary/alternative), 2) medications (prescription or over-the-counter), 3) interventions (injections, surgery, etc.), or testing (x-rays, MRI, etc.), and 4) lost time from work or decreased work productivity. Conditional logic will be used to reduce response burden for patients not seeking any care. Patients who are seeking care will be given follow-up questions to ascertain the number and nature of utilization in each category in the past month.]*

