[We will train physical therapists in two outpatient clinics in the University of Utah Health Care system in the treatment program for EPT patients. These two clinics (University Orthopedic Center and South Jordan Health Center) provide good geographic coverage and have the necessary equipment to perform study treatments. There are 14 full-time physical therapists in these clinics that will be trained. New therapists will be trained on an ongoing basis. [name] and the coordinator will lead the training. [name] is experienced training therapists to successfully perform research-related treatments regardless of clinician experience.¹⁴² A written procedure manual including study logistics and treatment techniques will be developed and an inperson training session held prior to enrollment. This session will explain the research process including issues related to human subjects, research ethics and adverse event reporting. Treatment procedures outlined above will be described, demonstrated and practiced during the session. Passing a written test related to study procedures will be required before a therapist will be able to treat study patients. We will conduct follow-up therapist meetings every 6 months to discuss progress and review procedures. More frequent sessions will be held if needed. Treatment fidelity during the first 4 weeks will be monitored by identifying off-protocol interventions received at the 4-week follow-up. Fidelity for the EPT group will be monitored on two levels. Therapists will record patient's self-reported compliance with assigned exercises on the treatment form from each session (appendix C). These forms are uploaded into the web-based data collection system. The study coordinator will audit at least 20% of forms to identify any concerns regarding treatment fidelity during the study. Off-protocol events will be recorded and feedback given to therapists.

C.7 Subject Retention Procedures

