[We will use several strategies to enhance retention. At the time of obtaining consent we will clearly outline the time that will be required of participants. We will clarify for participants that study-related treatments will not be billed to them or their insurance. We will use reminder calls and e-mails for follow-up assessments. We will be in monthly contact with all participants via e-mail during the follow-up period to obtain cost and utilization data, helping to keep the participant connected to the study. The 4-week follow-up is done in person because this contact relatively soon after enrollment helps to maintain a sense of connection to the project for all participants, particularly those in the UC group. Long-term follow-ups are completed electronically to reduce the burden of an in person meeting. Our experience in our ongoing trial suggests this balance of in-person contact and the convenience of remote long-term follow-ups with frequent reminders and small gifts for completing assessments has been guite successful in retaining participants.

C.8 Data Management and Quality Control Procedures

Data will be entered into REDCap, a software toolset and workflow methodology for electronic collection and management of research and clinical trial data. REDCap provides secure and easy data manipulation with audit trails for reporting, monitoring and querying records, and an automated export mechanism to common statistical packages (SPSS, SAS, Stata) facilitating quicker time to analyses. Periodically during the study data will be exported by the University of Utah Study Design and Biostatistics Center (SDBC) at the University's Center for Clinical and Translational Science (CCTS). The database will be maintained on a server supplied and maintained by University of Utah Health Sciences Center. The SDBC, directed by coinvestigator [name], will provide additional analyses to monitor progress, including rates of recruitment, retention and adherence to study protocols.

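### EPT session costs are to be taken from patients' monthly diaries, although a therapist form is completed at each session and could supply the count

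*Protocol*

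**What the plan says.** Protocol C.5 (Healthcare Utilization and Direct and Indirect Costs) states: "We will use a cost diary method integrated into the web-based data collection system to collect utilization and cost data". C.9, Specific Aim #2, repeats this: "We will examine costs from a societal perspective, collecting both direct and indirect costs using cost diaries". No other source of cost data is named. On pricing, C.9 says "we will value cost data with standard unit prices", based on the University's clinical research billing rates. Missing costs are to be multiply imputed.

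The diary is monthly. It asks about resources used for low back pain in four categories, the first being provider visits. Conditional logic spares patients who are not seeking care from the detailed questions. The others are asked for the number and nature of what they used.

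C.6 plans 6-8 EPT sessions in the first 4 weeks, the period in which C.2 says the two strategies differ. The short-term cost-effectiveness analysis in C.9 uses costs over those same 4 weeks. C.7 adds: "We will clarify for participants that study-related treatments will not be billed to them or their insurance".

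C.6 (Therapist Training and Fidelity Monitoring) also describes a treatment form completed by the therapist at each session. Of these it says: "These forms are uploaded into the web-based data collection system". Their stated purpose is fidelity monitoring. No section uses them to count or cost sessions. Sections 1 to 4 of the SAP contain no cost analysis that would fill the gap.

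**The concern.** The plan relies on patient recall for the one cost component that the study itself delivers and records. Three features of the diary leave that component exposed.

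- **Recall.** A patient reports up to eight visits from memory over a month.
- **Non-reporting.** A patient who was assigned free sessions by a study may not think of them as care sought. Such a patient could answer no at the conditional-logic step and never reach the visit count.
- **Imputation.** The sessions are concentrated in the first month. If that diary is missing, the whole session cost for that patient is imputed, although a record of the sessions should exist.

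The protocol's own support for the diary does not reach these sessions. Its validity evidence is agreement with insurance claims, and unbilled sessions generate none. Its reassurance on missing diaries is that limited periods extrapolate well to a year, but later months carry no information on sessions delivered in weeks 1-4.

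At stake is the incremental cost at 4 weeks and at 1 year, and with it the cost-effectiveness ratio, the net benefit and the acceptability curve.

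**Working it through.** **Inputs from the documents.** Two sessions a week for two weeks, then 1-2 in weeks 3-4, 6-8 in total (C.6); 110 patients per arm (C.11); diary compliance 85%, taken from paper-based studies (C.5). The documents give no unit price, no expected cost difference and no reporting rate for study sessions, so results are left in sessions. Each session miscounted shifts that patient's cost by one unit price.

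**Step 1: reproduce the planned volume.** Reading the weeks 3-4 figure as per week:
- low: 2×2 + 1×2 = 6
- high: 2×2 + 2×2 = 8

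This matches the stated 6-8. Read as a total for both weeks, it would give 5-6, which does not match. For the arm under full attendance, 110×6 = 660 and 110×8 = 880 sessions.

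**Step 2: shortfall if a share u of sessions is left out of the diary.** Shortfall per patient = u × s, with s = 6 to 8; for the arm, multiply by 110. The values of u are assumptions.

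| Assumed u | Per EPT patient | EPT arm |
|---|---|---|
| 0% | 0 | 0 |
| 10% | 0.6-0.8 | 66-88 |
| 25% | 1.5-2.0 | 165-220 |
| 50% | 3.0-4.0 | 330-440 |

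If patients over-count, u is negative and the same formula gives an excess. The form-based count does not depend on u.

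**Step 3: volume exposed to imputation.** If 85% compliance applied to the first diary, and that diary covered all study sessions (both assumptions), 1 − 0.85 = 15% of EPT patients would have an imputed session cost. That is 0.15 × 110 = 16.5 patients, or 99-132 planned sessions. This measures how much recorded information is replaced by imputed values. It does not measure bias.

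**Step 4: is the count close enough to constant to be imputed safely?** The as-treated analysis in SAP Section 1 moves 10 of 110 EPT subjects to usual care, apparently because they did not receive EPT (the sentence seems to lack a negative), and 5 of 110 usual-care (UC) subjects the other way. Delivery therefore varied between patients. Session forms would show this directly; an imputation model could only predict it.

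**The case against.** A reader might infer that EPT cost is likely to be understated, in one arm and one direction, so that EPT is made to look cheaper. The documents do not support that, for these reasons:

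- The diary asks about resources used, with provider visits first. It does not ask about bills or payments, and reported visits are priced at standard rates. Lack of billing therefore does not itself remove the cost. With full reporting the shortfall is zero, and recall can also over-count.
- The 85% compliance figure is not specific to either arm. Missing costs are multiply imputed, and C.9 plans separate analyses for patients with complete and with imputed costs. Imputing a countable quantity wastes information but does not by itself favour EPT.
- The diary form (Appendix A) and treatment form (Appendix C) are not in the available text, so a dedicated item for study physical therapy cannot be ruled out.
- It is tempting to say the sessions make up most of the cost difference. The 4-week analysis also includes lost productivity of unknown size, and over 1 year the protocol expects differences in MRI and injection use.
- The forms may be incomplete. C.6 describes them mainly as a record of exercise compliance, with an audit of at least 20%. A lost form would itself lower EPT cost.

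All of this stands. It rules out a claim about direction or size, and it argues against relying on the forms without a check. It does not answer the narrower point: for the component where the arms are designed to differ, the plan uses recall when a contemporaneous record is already in the data system, and it names no check of one against the other.

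**Conclusion.** The point holds as a weakness in how a key cost component is measured. The diary is the only named source of direct costs, the EPT sessions fall inside the 4-week cost-effectiveness window, and a per-session therapist record is collected but not used for costing. Counting from the forms is a better method than the one stated and needs little extra work.

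The size and sign of any error are unknown. The illustrative range is no shortfall with full reporting, 0.6-0.8 sessions per EPT patient at 10% omission and 3.0-4.0 at 50%, and an excess if patients over-count. These figures assume full attendance and the planned 6-8 sessions; the omission shares are not from the documents. The effect is confined to the Aim 2 cost and cost-effectiveness results. The primary comparison of Oswestry change at 6 months is unaffected. The change should be made, but the point does not threaten the trial's main conclusion.

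**What to change.** State in C.5 and in C.9, Specific Aim #2, that:

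1. Study-delivered EPT sessions are counted from the per-session treatment forms and valued at the standard unit price.
2. The diary is used for all other care in both arms.
3. A diary-reported physical therapy visit is removed only when it matches a study session form for the same patient. UC visits without a form are kept. This matters because C.4 foresees UC patients reaching a trained clinic, and SAP Section 1 counts 5 who received the intervention. Deleting every early visit to the study clinics would wrongly lower UC cost.
4. Where forms are missing, the diary count is used; failing that, the count is imputed.
5. A sensitivity analysis repeats the cost comparison with diary-based counts.

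The cost is a few sentences of text, a merge of records already in the data system, a matching rule and a check of form completeness. Matching also needs a diary item that separates study physical therapy from other visits, since C.5 describes only monthly number and nature, not clinic or date. If costs have already been analysed, form-based counts can be reported as a sensitivity analysis.

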Patients in the EPT group will receive the same education and advice intervention described above and will receive physical therapy during the initial 4 weeks following enrollment. Physical therapy treatment will be standardized based on evidence and our prior research evaluating a centralizing treatment program for the sub-group of patients with LBP and sciatica. The first physical therapy session will be scheduled within 3 days after enrollment and 6-8 sessions will be administered within the first 4 weeks [*in a clinic trained to provide the study treatment*] (2 weekly sessions in first two weeks and 1-2 sessions in weeks 3-4 based on therapist judgment). Each session will include a brief assessment and treatment with centralizing exercises

and spinal mobilizations. Mechanical traction is an optional component. Centralizing exercises will progress according to table 3, and consist of sustained and repeated movements to extend the spine as this most often produces centralization. Modifications can be made by the therapist to maximize centralization. Therapists will instruct patients to monitor symptoms and perform exercises in a range to maximize centralization and minimize discomfort. Patients will be provided handouts and instructed to perform assigned exercises at home every 4-5 hours on days between sessions. Spinal mobilizations will be performed with the patient prone or side-lying with varied amplitude and velocity to promote centralization of symptoms and spine extension. If mechanical traction is used it will be applied using a 3D ActiveTrac device (Empi, Minneapolis). We have used this 1. Lying on stomach 5. Prone press-up to extended arms with sag device in prior studies and have access in our 2. Propping on elbows 6. Prone press-up to extended arms with overpressure facilities. Static mechanical traction is applied for a 3. Prone press-up to 7. Repeated extension in standing maximum of 12 minutes with force parameters and A Prone press-up to extended arms elbows patient positioning adjusted to maximize symptom Goal: Tolerate for 5 minutes or 3 sets of 10 repetitions to maximize centralization centralization.

 Table 3. Progression of Centralizing Extension Exercises

Therapist Training and Fidelity Monitoring

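### The cost analysis is labelled societal, but the listed diary items leave out travel and patient time outside work, an omission probably larger in the EPT arm and likely to favour EPT at 4 weeks

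*Protocol*

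**What the plan says.** Protocol C.9, Specific Aim #2, sets the perspective: "We will examine costs from a societal perspective, collecting both direct and indirect costs using cost diaries". Direct items are priced from University research billing rates ("we will value cost data with standard unit prices"). Lost work is valued at the patient's salary. The calculation extends beyond paid employment: "Patients not employed outside the home (homemakers, students) will report absenteeism and presenteeism", valued at matched average pay.

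Protocol C.5 describes the instrument: "Each monthly cost diary will ask patients if they have utilized healthcare resources in the past month specifically for LBP in 4 categories". The first three categories are "1) provider visits (traditional or complementary/alternative), 2) medications (prescription or over-the-counter), 3) interventions (injections, surgery, etc.), or testing"; the last is "4) lost time from work or decreased work productivity". Follow-up questions then establish how much was used and of what kind. The diary form is in an appendix that was not supplied.

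Protocol C.6 states the EPT schedule: "6-8 sessions will be administered within the first 4 weeks", at a clinic trained for the study (two are named). UC has no scheduled treatment visit in that window. Patients in both arms may go back to primary care as needed.

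C.9 plans a short-term cost-effectiveness analysis on costs in the first 4 weeks and a long-term one at 1 year. The planned cost sensitivity analyses vary how direct and indirect costs are valued and name no additional cost item. The SAP as supplied describes no cost analysis.

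**The concern.** A societal perspective ordinarily includes what patients themselves give up to obtain care. Two such items, travel and time outside work, do not appear in the listed categories. A third, working time spent at treatment, is left undefined: the protocol counts days absent and reduced performance at work because of back pain, and does not say where an hour or two at a clinic belongs.

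This would matter little if the two arms made similar numbers of visits, but the design makes them differ. EPT patients are scheduled for 6-8 sessions in exactly the 4 weeks that the short-term analysis covers. C.7 says study treatment is not billed to patients or their insurers, so time and travel are a main part of what patients still bear for these sessions. C.13 itself names access to the physical therapy clinics as a possible limitation.

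The planned safeguards would not reveal the gap. Re-valuing listed items leaves an unlisted item at zero, and the probabilistic analysis puts distributions on measured costs, so the item is zero in every draw. The effect would be a shift in the cost difference, the net benefit and the acceptability curve, with no added width to signal it.

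**Working it through.** **Inputs from the documents**
- Session schedule (C.6): two per week in weeks 1-2, one or two per week in weeks 3-4.
- Treatment received (SAP section 1): 10 of 110 EPT patients are moved to UC in the as-treated analysis, and 5 of 110 UC patients are moved to EPT. The SAP sentence says the 10 did receive the intervention. I read it as meaning they did not, since otherwise the move makes no sense.

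**Inputs assumed, because the documents give none**
- Main illustration: 1.25-2 hours door to door per session, valued at $20-30 per hour.
- Travel: round trip of 5-40 miles at $0.20-$0.60 per mile, with a middle case of 20 miles at $0.50.
- Anyone who received EPT attended the full 6-8 sessions.

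**Step 1: reproduce the stated number of sessions.** 2×2 + 1×2 = 6 and 2×2 + 2×2 = 8. The stated 6-8 follows from the schedule.

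**Step 2: value of time per patient who attends all sessions.** Sessions × hours × hourly value:
- low: 6 × 1.25 × $20 = $150
- high: 8 × 2 × $30 = $480

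**Step 3: difference between arms as randomised.** Receipt was 100/110 in EPT and 5/110 in UC, a net 95/110 = 0.864.
- Sessions: 6 × 0.864 = 5.2 and 8 × 0.864 = 6.9 per patient.
- Time: $150 × 0.864 = about $130 and $480 × 0.864 = about $415 per randomised patient.

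This is before subtracting other UC visits and any session time already reported as lost work. Travel expense is extra.

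**Step 4: lower limit if all session time is already in the lost-work item.** Only travel remains, per patient attending all sessions:
- low: 6 × 5 × $0.20 = $6
- middle: 6 × 20 × $0.50 = $60 to 8 × 20 × $0.50 = $80
- high: 8 × 40 × $0.60 = $192

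**Step 5: wider range, time plus travel, with no time already counted.**
- low (1 h, $10/h, 5 miles at $0.20): 6 × ($10 + $1) = $66
- high (2.5 h, $35/h, 40 miles at $0.60): 8 × ($87.50 + $24) = $892

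Multiplied by 0.864, these are about $57 and $770 per randomised patient.

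**Step 6: what would cancel it.** At one common unit cost per visit, the omission balances if UC patients make on average 5.2-6.9 more other visits than EPT patients over the period analysed. That would be a lot of as-needed primary care in 4 weeks. Over a year of further care and referrals it cannot be ruled out.

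**The case against.** Several points on the other side stand.

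- **A reader might infer that the diary ignores patient time altogether.** It does not. The fourth category collects lost work, and homemakers and students report it too. Some or all session time taken from work may already be counted.
- **A reader might infer that the cost is understated in one arm only.** UC patients also travel and spend time on visits, other referrals are not controlled, and 5 of 110 received EPT. The difference between the arms is one of amount.
- **A reader might infer a bias towards EPT at every horizon.** Aim 2 hypothesises less MRI and injection use with EPT over 1 year. If so, unpriced time and travel for that extra UC care would offset part of the gap, and the 1-year direction cannot be read from the documents.
- **A reader might infer that the cost-effectiveness conclusion would change.** The documents give no total cost, cost variance or willingness-to-pay value, so nothing shows that it would.
- **The form itself was not supplied.** Its follow-up questions may ask for more than the text lists. The point concerns the plan as written.

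It can also be said that the protocol openly states what it counts, so this is only a matter of labelling on a secondary aim. That is fair for severity. It does not remove the point, because a result presented as societal will be read as including what patients bear, and the two strategies differ in that burden by design.

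**Conclusion.** The point holds in limited form. The stated perspective is wider than the listed measurements, which omit travel and patient time outside work and leave time attending treatment undefined. Because EPT requires 6-8 sessions in the first 4 weeks, the omission is probably larger in EPT and likely favours EPT in the 4-week analysis. The net effect at 1 year is uncertain.

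The size cannot be derived from the documents. About $130-$415 per randomised patient rests on the assumed hours and hourly values, on reading the 10 EPT patients as untreated, and on full attendance by those treated. It is reduced by other UC visits and by session time already reported as lost work; if all of that time is already counted, only travel remains. The point affects Aim 2 costs and cost-effectiveness only, not the primary 6-month OSW comparison or the sample size.

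**What to change.** Choose one of two changes.

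1. **Add a sensitivity analysis.** Apply a standard time-and-travel unit cost to every recorded visit in both arms. Take EPT sessions from the session treatment forms that C.6 says are uploaded, and other visits from the diary, counting each session once if a patient also entered it as a provider visit. Run it with and without the time component for employed patients, so that the two results bound any double counting with lost work. Homemakers and students also report lost productivity, so the same pair of runs should cover them. State in the text whether time attending treatment is meant to count as lost work.
2. **Restate the perspective** as health-care cost plus lost productivity, and limit the conclusions to that.

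Home-exercise time need not be part of either change.

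The first is a desk costing step on visit counts that the plan already collects. No travel distance is listed as collected, so the unit cost must be assumed and varied, and EPT may look somewhat more expensive. The second costs a reworded sentence and a narrower claim.
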